A strong body of literature supports the assertion that a subspecialty infusion center (IC), staffed by expert clinicians and delivering individualized care, can improve care quality while reducing costs. Benjamin et al. found that establishment of a dedicated SCD day hospital led to a 40% reduction in inpatient admissions relative to ED management.²⁴ Since this seminal finding, a number of supporting papers have confirmed that rapid assessment of VOC, close monitoring, social service support, and individualized care improves outcomes.²⁵⁻²⁸ Yet there has never been a direct comparison between IC clinics and the ED setting.

The purpose of this study is to compare outcomes between IC and ED settings in four locations around the US.

2. Objectives (include all primary and secondary objectives)

Primary outcome- time from arrival to first dose of parenteral pain medication.

Secondary outcomes:

- Outcome of acute visit – admission v discharge home
- Was patient reassessed 30 minutes after their first dose of pain medication
- Assess patient reported satisfaction and patient reported perceptions of risk (e.g. from medical errors)

3. Background (briefly describe pre-clinical and clinical data, current experience with procedures, drug or device, and any other relevant information to justify the research)

Sickle cell disease (SCD) is a genetic disorder of the blood that leads to severe morbidity and early mortality. It is the most common disease detected by newborn screening efforts in the United States (U.S.).¹ Between 80,000 and 100,000 individuals in the U.S. are affected by some form of SCD.² African-Americans (AA) are most affected in the U.S., as 1 per every 400 AA newborns is born with the disease. The damage SCD inflicts on sufferers is dramatic. The disease reduces life expectancy by approximately 30 years compared to the general population.³ Furthermore, **the disease limits quality of life - as severely as does end-stage renal disease requiring hemodialysis.**⁴

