The purpose of this study is to compare patient centered outcomes for those patients being treated for an uncomplicated VOC in ICs and EDs. We have designed this study based on preliminary, single site retrospective data on ICs from our participating sites which have shown similar outcomes to that of Benjamin²⁴. The Johns Hopkins Sickle Cell Infusion Center (SCIC) which opened in 2008 provides acute care solely for adults with SCD. In 2008, 50% of all ED visits for VOC resulted in hospital admission at Johns Hopkins Hospital (JHH). The SCIC initially was opened 5 days a week and in 2011 increased hours to include the weekends. The SCIC has 5 treatment slots for acute care visits, and is staffed by a clinic coordinator, nurse, clinical nurse associate, social worker and physician extender. Supervision is provided by [name], who is the medical director and the proposed PI for this study. From the period February 2008 through December 2011 there were 3874 visits to the SCIC by 361 unique patients. On average, there were 3.8 visits to the infusion clinic daily (range 0-10). The average number of visits by each individual was 10 (range 1-84) or 2.5/yr. Eighty five percent of visits ended with the patient being discharged home. The remainder were either directly admitted to the hospital or sent to the ED for further treatment. *The average time to receipt of first dose of opioid from arrival to the clinic was 57.7 minutes* (95% CI 56.5, 58.8). The average time that patients spent in the SCIC was 4 hours and 55 minutes. The average pain level on arrival using the numerical rating scale (NRS), which measures pain on a scale of 0-10, was 8.4 (95% CI 8.3, 8.4). The average decrease in pain score from arrival to discharge was 2.62 points on the NRS (95% CI 2.55, 2.69). Those who went home had a significantly greater decrease in pain than those that remained for hospital care (Δ -2.9 vs. Δ -1.2, $p<0.001$). There was borderline statistical but no clinically significant difference in time to first dose of opioid for patients who were discharged home compared to those that required additional hospital care (57.2 min v 60.3 min, $p=0.06$). In examining the association of changes in pain scores with discharge disposition, we found that, after adjusting for gender, patients were 2 times (OR 2.01, 95% CI 1.85, 2.19) more likely to be discharged home for every 1 point decrease in their pain. In comparing these outcomes to the JHH ED between 4/2010-7/2012, there were 1554 total ED visits for SCD pain made by 254 unique patients. *In the ED, the average time from triage to first dose of pain medication during this time period was 190 minutes* (SD 129.8). In a model controlling for acuity in the ED, for every 10 minute increase in time to first dose of pain medication, the relative risk of admission increased by 0.7% (95% CI 1.00 1.01, $p=0.024$). Since the opening of the SCIC there has been a 22% reduction in admissions and reduction in 30 day readmissions from 39% to 22%.

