
A similar clinic to the SCIC opened at Froedtert Hospital in Milwaukee (FASCC) in 2011. The FASCC clinic is open weekdays and serves the needs of 300 adults with SCD. The average length of stay in the clinic is 3 hours and 96.5% of visits end with the patient being discharged home. Since this clinic opened there has been a 38% decrease in admissions and a decrease in 30 day readmissions from 61 to 28%.

Without a direct comparison of ED to IC, many argue that there is something different about the patients that receive care in an ED versus those that seek care in an IC. Further, the recent expansion in ICs has been driven primarily by economic consideration (length of stay, readmissions), rather than by patient-centered outcomes, on which there is a lack of data. Demonstrating attainment of important clinical outcomes in ICs may increase their stability and viability. **With this proposal we will demonstrate that the improved outcomes seen in an IC v. the ED are not due to differences in the type of patients seen for care but rather in the processes of care for VOC in these two sites.**

4. Study Procedures

- a. Study design, including the sequence and timing of study procedures (distinguish research procedures from those that are part of routine care).

We will prospectively enroll patients that are seen in participating centers into a study cohort. We will then capture data from their acute visits. We will enroll participants from 4 sites: Baltimore, Cleveland, Milwaukee and Baton Rouge. When any participant is treated in either an ED or IC, data on clinical outcomes and patient experiences of care will be collected.

Baseline data collection will include: SCD genotypes and co-morbidities³⁵

- a. AVN
- b. Gall bladder disease
- c. Sickle chronic lung disease
- d. Leg ulcer
- e. Priapism (male)
- f. Renal failure
- g. Retinopathy
- h. Stroke

2. Self-reported number of acute care visits and hospitalizations in the prior 12 months
3. Daily chronic pain using the Numeric Rating scale (NRS).
4. Prior and current treatments, including:
 - a. hydroxyurea use
 - b. chronic transfusions
 - c. pain medications, (specific regimens used to treat chronic daily or intermittent pain)

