After participants have consented they will be asked to contact by phone or email the research assistants about all acute care visits. In addition, the research assistant will review the daily census for IC's and ED's at the local site to identify participants with an acute care visit. Furthermore, each participant will be contacted by phone monthly and asked about acute care visits.

Once an acute care visit for an uncomplicated VOC has occurred, the following data will be collected: Time crisis started, Arrival time, Triage time, Pain level on arrival, Time to first dose of opioid, Time from first dose to nurse reassessment of pain, Time in the ED/IC, Pain level at discharge from ED/IC, Change in pain scale from arrival to discharge, Disposition at time of discharge from ED/IC (home, admit, etc.). In order to assess patient experiences of care in the acute setting, participants will be surveyed either toward the end of their acute visit or by phone within 72 hours of their visit. As reinforcement, at each monthly call, we will verify contact information and encourage participants to call us within 3 days of any acute visit. The survey tools that will be used include the Painful Crises Experiences of Care for SCD tool (PEPS); a survey of safety and a survey of patient satisfaction with ED pain management.

- b. Study duration and number of study visits required of research participants. Participants will be part of the study for 18 months. During which time there will be no in person study visits. There will be monthly phone calls and contact at the time of acute care visits.
- c. Blinding, including justification for blinding or not blinding the trial, if applicable. NA
- d. Justification of why participants will not receive routine care or will have current therapy stopped. NA
- e. Justification for inclusion of a placebo or non-treatment group. NA
- f. Definition of treatment failure or participant removal criteria. NA
- g. Description of what happens to participants receiving therapy when study ends or if a participant's participation in the study ends prematurely. NA

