Given the anticipated differences in patients who seek care in these settings, we propose using propensity score techniques to balance patient characteristics in the two treatment groups both within and across sites. We will use relatively new methods developed for use of propensity scores in the context of multilevel data.⁴² We look towards using propensity scores for achieving balance in the distributions of covariates to allow for a causal comparison. Our treatment assignment is at the individual level and we propose using appropriate propensity weighting methods to generate valid causal inferences, under the assumption of absence of unmeasured confounders.

For causal comparisons, we adopt the potential outcome framework for causal inference.⁴³ Under the standard stable unit treatment value assumption (SUTVA)⁴⁴, which states that the outcomes for each patient are unaffected by the treatment assignments of the other patients, each patient has two potential outcomes corresponding to the two treatments (ED or IC care), only one of which is observed for each patient. We believe the SUTVA assumption to be true in our setting. We aim to estimate the population average treatment effect, although we may also look at the *population average treatment effect on the treated (ATT)*, which we expect will be very similar.

Notation Let $k = 1, 2, \dots, K$ denote number of regions and $i=1, 2, \dots, n_k$ denote the number of participants in region k . Total sample size is $n = \sum_{k=1}^K n_k$. Each subject belongs to one of two groups, ED (control) or IC (treatment) care. Let Z_{ki} be the binary variable indicating whether the subject is in the treatment ($Z=1$) or control ($Z=0$) group. Also, let U_{ki} be a vector of subject-level covariates and V_k be a vector of region-level covariates, and $X_{ki} = (U_{ki}, V_k)$. For each subject, an outcome Y_{ki} is observed, which, in our study, can be continuous or binary. The propensity score is defined as $e(X_{ki}) = \Pr(Z_{ki}=1 | X_{ki})$.

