To test the first hypothesis (time to pain medication), we will use the observed time to first dose (a continuous outcome) in the two groups. We do not need to use time-to-event models since there will be no censoring. We will evaluate whether the time needs to be log-transformed in order to be approximately normally distributed. To test the second hypothesis, we will describe the proportion of patients in each group that is reassessed in the first 30 minutes after dosing. We will describe the proportion of patients admitted in each of the treatment groups, using the estimator described above. For evaluations of the difference in *patient experience* of care in these two settings this likely reflects the adequacy of symptom relief during the visit and the patient-centeredness of the visit including being treated respectfully and feeling unthreatened in the environment. The outcome of interest is an ordinal measure on a scale of 18 points that we will analyze as a continuous outcome, using the estimator above. The other surveys will be analyzed similarly.

Sensitivity analysis In our sensitivity analyses, we will stratify patients into quintiles based on their propensity scores and test for differences in the outcomes of interest between ED and IC treated patients in each quintile. These quintile-specific estimates will be reported, as well as pooled estimates from application of random effects methods.

We will also estimate propensity scores using a fixed effect model rather than a random effects model (Eq 2). We might also explore the use of a doubly robust estimator, where we would model the potential outcomes using a random effects model. The results are expected to be similar.

We will also test whether our inferences are sensitive to hidden biases from unmeasured confounders. We will estimate how strong an unmeasured confounder needs to be related to both exposure and outcome to affect the inference about difference in effect in the treatment sites. Potential unmeasured confounders might be patient-preference for site of care, or local culture or climate regarding care of patients with SCD.

a. Statistical plan including sample size justification and interim data analysis.

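### Admission is read only at exit from the ED or IC, so later admissions for the same crisis are missed; since more IC patients go home, this probably overstates the IC benefit

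*Combined protocol and SAP*

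**What the plan says.** Section 2 lists the secondary outcome as "Outcome of acute visit – admission v discharge home". Section 4a gives the data item behind it: "Disposition at time of discharge from ED/IC (home, admit, etc". No window after discharge is given, no crisis episode is defined, and no rule says how two visits in one crisis are handled. Section 3 reports that some Baltimore IC patients were sent on to the ED, but Section 4a does not say how such a transfer is coded.

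The analysis in Section 7 is written per person: "Each subject belongs to one of two groups, ED (control) or IC (treatment) care" and "For each subject, an outcome Y_{ki} is observed". For admission it says "We will describe the proportion of patients admitted in each of the treatment groups", using the weighted estimator. Section 4a, however, collects data at every ED or IC treatment over 18 months, and Section 7 does not say which visit supplies a person's group and outcome.

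Section 7a bases the sample size on admission rates of 50% (ED) and 27% (IC).

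**The concern.** Section 7 aims at a causal statement about the setting of care. Exit disposition shows whether the patient was admitted before that visit ended. It does not show whether the crisis led to admission. The two differ when a patient goes home, comes back for the same crisis and is then admitted.

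Such returns are plausible after IC care. For Baltimore, "The average time that patients spent in the SCIC was 4 hours and 55 minutes"; for Milwaukee, "The average length of stay in the clinic is 3 hours", and that clinic opens on weekdays only. Someone sent home from Milwaukee on a Friday who worsens at the weekend cannot return to the IC.

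The rule is the same in both arms but does not act equally on them, because only patients sent home can have a missed admission and the plan expects many more of those in the IC arm. At stake is the size of the claimed reduction in admissions.

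**Working it through.** **Inputs from the documents.** ED admission 50% and IC admission 27% (Section 7a), taken here as exit rates. The planned gap is 50 − 27 = 23 points. Sent home: 100 − 27 = 73% of IC and 100 − 50 = 50% of ED patients.

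**Assumed inputs (not in the documents).** Return for the same crisis after discharge home: r = 5%, 10% or 20%. Admission at that return: a = 50% to 70%, the same in both settings.

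**Step 1. Crisis-level rates.**
- IC: 0.27 + 0.73 × r(IC) × a
- ED: 0.50 + 0.50 × r(ED) × a
- Overstatement of the gap by exit scoring: a × (0.73 × r(IC) − 0.50 × r(ED))

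**Step 2. One outcome per index visit.** With equal return rates the overstatement is 23 × r × a points. If only IC discharges return, it is 73 × r × a points.

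| r | a | Overstatement, equal returns | Overstatement, IC returns only | Crisis-level gap, IC returns only |
|---|---|---|---|---|
| 5% | 50% | 0.6 | 1.8 | 21.2 |
| 5% | 70% | 0.8 | 2.6 | 20.4 |
| 10% | 50% | 1.2 | 3.7 | 19.4 |
| 10% | 70% | 1.6 | 5.1 | 17.9 |
| 20% | 50% | 2.3 | 7.3 | 15.7 |
| 20% | 70% | 3.2 | 10.2 | 12.8 |

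With equal returns the crisis-level gap is 22.4 to 19.8 points.

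**Step 3. Where the direction changes.** The bias is zero when 0.73 × r(IC) = 0.50 × r(ED), that is r(ED) = 1.46 × r(IC). With r(IC) = 10%, r(ED) = 20% and a = 50%, it is 0.5 × (7.3 − 10.0) = −1.35 points, so exit scoring would then understate the IC benefit. The home-discharge rates in Section 3 (85% Baltimore, 96.5% Milwaukee) against 50% for the ED put the break-even at 1.7 and 1.9 times.

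**Step 4. If visits were pooled and IC returns entered the ED arm as new observations** (equal index visits per arm, only IC discharges return). The observed ED rate is (0.50 + 0.73 × r × a) / (1 + 0.73 × r).
- At a = 50% the observed gap stays at 23.0, because returns are admitted at the ED's own rate. The distortion is as in Step 2.
- At a = 70% the observed gap is 23.7, 24.4 or 25.5 for r = 5%, 10% or 20%, against crisis-level gaps of 20.4, 17.9 and 12.8. At r = 20% the overstatement is 12.8 points, compared with 10.2 in Step 2.

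**Step 5. Power for a crisis-level gap.** Take the stated 205 per arm and the design effect 1 + (41 − 1) × 0.02 = 1.8, from the stated 41 per cluster and ICC of 0.02. Two-sided 5% power is about 0.95 for 23 points, 0.85 for 19.4 and 0.67 for 15.7.

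**The case against.** The best defence is that exit disposition is exactly the outcome that Section 2 names, applied alike to both settings, and that it is secondary to time to first dose. That stands as far as it goes: the item is a valid description of a visit and should stay. It does not support a causal claim that IC care reduces admissions, because the shares at risk of a missed admission differ by design.

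Four stronger readings are tempting, and the documents do not support them.

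- *The plan counts the return as a fresh ED visit.* It never says so. Section 7 has one group and one outcome per subject. Collecting every visit is not an analysis rule, so Step 4 is a conditional case. Equally, nothing in the plan rules it out.
- *The IC benefit is certainly inflated.* ED patients sent home can return too, and Step 3 shows a reversal. After the ICs opened, 30-day readmissions fell from 39% to 22% (Baltimore) and from 61% to 28% (Milwaukee). These are before-and-after figures and do not measure return after IC discharge, but they give no sign of more returns.
- *Patients leave the IC with an unresolved crisis.* Section 3 says "Those who went home had a significantly greater decrease in pain than those that remained for hospital care" and gives a fall of 2.9. Taking that from the arrival mean of 8.4 gives 5.5, but 8.4 is the mean over all visits, and chronic daily pain may leave a non-zero baseline.
- *IC stays are short compared with the ED.* No ED length of stay is given. Baltimore's IC has also opened at weekends since 2011, so the weekend argument applies to Milwaukee only.

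**Conclusion.** The concern holds in a limited form. The plan fixes admission at exit from a single visit, and a later admission for the same crisis is lost to the first setting. With 73% against 50% sent home, this probably, but not certainly, overstates the IC benefit.

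Of the planned 23 points, the overstatement is 0.6–3.2 with equal return rates and 1.8–10.2 if only IC discharges return. It would be larger if visits were pooled and returns were admitted more often than the ED average. All of these sizes rest on assumed return and admission-at-return rates and on reading 27% and 50% as exit rates. The change should be made before analysis. It does not touch the definition of the primary outcome.

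**What to change.** - Keep exit disposition as stated. Add an episode-level outcome: hospital admission within a fixed window, such as 72 hours, of arrival at the first ED or IC visit of the crisis, attributed to that first setting and applied identically in both arms.
- Link visits by the crisis start time already collected in Section 4a, together with the window.
- State that a same-crisis return or an IC-to-ED transfer is not a new ED exposure, and say which visit supplies each subject's group and outcome.
- Base any claim that IC care reduces admissions on the episode-level result, and restate the 27% and 50% planning rates for that outcome.

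The cost is protocol and SAP wording plus linkage of visits that are mostly captured already by census review, participant contact and monthly calls. There are three downsides. The admission benefit may come out slightly smaller. A few new crises inside the window may be merged with the previous one. Census review covers only the local site, so returns elsewhere depend on participant report.

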There continues to be a wide variation in how acute painful events are diagnosed and managed in the acute setting because management of VOC has never been studied in a systematic fashion (RQ-1). There are no objective clinical or laboratory measures of the presence or severity of a crisis, and so the only way to confirm that a patient is having a crisis is to ask the patient (i.e., patient self-report). The current pain scales used for self-report have not been validated in this patient population.²⁹ It is therefore not surprising that due to this uncertainty many patients receive suboptimal care in the acute setting, especially when managed by clinicians, as in the ED, who are unfamiliar with them and who are not trained to specifically manage their disease and its complications.

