All data collection will be done using RedCap. RedCap is a secure web based database tool that has multisite functionality. Each external site will enter their data into a single database. Each external site will only have access to their own data through the site. As the central coordinating site, Hopkins will have access to all of the data. When data collection is complete and records are finalized the data will undergo data lock. As all data will be entered into a common database merging of data will be done after data is exported from RedCap into Stata for further analysis. Merging of data will need to be done for combining the demographic data with data collected from each acute visit.

5. Inclusion/Exclusion Criteria

All individuals with confirmed SCD who live within 60 miles of the study center or who already receive regular care at the participating centers will be eligible for enrollment. The only exclusions will be patients who are pregnant, who have been stable on chronic transfusion therapy and have not had a painful episode within two years of enrollment (transfusions may prevent all acute painful events) and patients who are unwilling or unable to sign consent.

6. Drugs/ Substances/ Devices

- a. The rationale for choosing the drug and dose or for choosing the device to be used. NA
- b. Justification and safety information if FDA approved drugs will be administered for non-FDA approved indications or if doses or routes of administration or participant populations are changed. NA
- c. Justification and safety information if non-FDA approved drugs without an IND will be administered. NA

Date: _____
 Principal Investigator: _____
 Application Number: _____

7. Study Statistics

Primary and secondary outcome variables: This is an observational study from which we will draw inferences about outcomes of care attributable to the treatment setting. As we are not randomizing patients to ED care or to IC care, we must control for confounders in the relationship between site of care and outcomes. We note, however, that there may be regional differences that impact on outcomes: percentage of high utilizers in the region, duration IC has been functioning, and ED crowding. In our study, we have clustering of individual patients by regions (n=4). We will account for both known and unknown confounders at the level of the regions.

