Fitting a Propensity Model Given the multi-region (clustered) data, we cannot use standard techniques for propensity score modeling but instead will use a *random effects model* that accounts for clustering. We have chosen this model because we are uncertain about all of the cluster-level covariates that might impact on treatment effect. The few that we hypothesize to be regional-level confounders, as described above, we will include in the model. The individual level covariates will include: SCD complications, self-reported number of acute care visits and hospitalizations in the prior 12 months, pain rating upon first arrival for care, distance from residence to site of care, and demographic variables. The random effects model to generate the propensity score is as follows:

$$\text{logit}(e_{ki}) = \delta_k + X_{ki} \beta \quad (1)$$

This model includes individual level covariates, as well as cluster-specific intercepts due to measured and unmeasured cluster-level covariates, and a prior distribution for cluster-level main effects, $\delta_k \sim N(0, \sigma_\delta^2)$. We expect that since we will have many patients within each region (cluster), we should not have any difficulty in fitting the random-effects model. The goodness of fit of this model will be checked by conventional diagnostics of covariate balance between the ED and IC treated patients, checking the overall and within-region balance of the weighted distribution of covariates in the two groups.

Estimating an Overall Treatment Effect We will then use the inverse of the propensity score, e_{ki} , generated from the random effects model described above, to *weight the outcomes* for each individual. This will allow us to draw valid inferences about the differences between groups. We propose using a non-parametric clustered-estimator as our inverse-probability-weighted estimator.

$$\hat{\pi} = \frac{\sum_{k=1}^K \hat{\pi}_k w_k}{\sum_k w_k} \quad (2)$$

Where $w_k = \sum_{i \in k} w_{ki}$, $w_{ki} = Z_{ki}/e_{ki} + (1-Z_{ki})/(1-e_{ki})$, and $\hat{\pi}_k$ is the inverse-propensity weighted treatment effect for the k -th region. This estimator accounts for clustering of the patients by region. The standard error of the estimate will be generated by bootstrapping.

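### Regular care at the center is a route into the study but is neither recorded nor adjusted for, so residual confounding by it cannot be excluded

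*Combined protocol and SAP*

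**What the plan says.** Section 5 (Inclusion/Exclusion Criteria) opens the study to people with confirmed sickle cell disease "who live within 60 miles of the study center or who already receive regular care at the participating centers will be eligible for enrollment". The two routes are joined by an or. Section 4a describes recruitment more narrowly: "We will prospectively enroll patients that are seen in participating centers into a study cohort".

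The baseline list in Section 4a begins "Baseline data collection will include: SCD genotypes and co-morbidities" and names eight conditions. It continues with "Self-reported number of acute care visits and hospitalizations in the prior 12 months", a daily chronic pain rating, and "Prior and current treatments, including" hydroxyurea, chronic transfusion and pain medication.

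For the propensity model (Section 7, Fitting a Propensity Model) the plan states: "The individual level covariates will include: SCD complications, self-reported number of acute care visits and hospitalizations in the prior 12 months". It then adds pain on arrival, distance from home, demographics and a few regional factors. Section 7 makes its causal reading conditional on there being no unmeasured confounders. Its sensitivity analysis will ask how strong a hidden confounder would have to be, and offers preference for a site and the local culture of care as possible examples.

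The end of Section 3 reports that "many argue that there is something different about the patients that receive care in an ED versus those that seek care in an IC", and commits the study to showing that better IC outcomes come from how care is delivered and not from who receives it.

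**The concern.** Whether a person is already followed by the center is settled before any acute visit, and it is one of the two facts that can make that person eligible. It could plausibly influence which setting the person uses, and also how quickly they are treated and whether they are admitted. If it did both, part of any weighted IC-ED difference would reflect who was already an established patient.

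A critic of the finished study would naturally ask whether the IC users were simply the center's own patients. Under the current plan no data would be collected to answer that directly. This matters more here than in most observational plans, because ruling out patient type is the stated purpose.

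**Working it through.** **Step 1. Set the lists side by side.**

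| Place | Content | Regular-care status |
|---|---|---|
| Section 5, eligibility | Address within 60 miles, or regular care | Present, as one of two routes |
| Section 4a, baseline list | Genotype, co-morbidities, prior-year use, chronic pain, treatments | Absent |
| Section 7, Eq 1 covariates | Complications, prior-year use, arrival pain, distance, demographics, regional factors | Absent |
| Section 7, sensitivity analysis | Site preference, local culture (as examples) | Not named |

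The weights are built from Eq 1, and the balance checks examine measured covariates. A variable in neither list is balanced only so far as the listed covariates carry it.

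**Step 2. Ask how far the listed covariates carry it.** Beyond 60 miles, regular care is the only way in, so distance identifies status exactly. Within 60 miles both groups are eligible and distance does not separate them. Prior-year counts are self-reported and not specific to the study center. Hydroxyurea and other treatments might be markers of follow-up, but they are collected without being named in Eq 1. These are partial proxies.

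**Step 3. Express the possible bias.** Suppose the setting has no effect. Let established patients have admission risk r1 and others r0, the same in both settings. Let p(IC) and p(ED) be the shares of established patients in the two groups *after weighting*. The weighted admission rates are r0 + p(IC)(r1 − r0) and r0 + p(ED)(r1 − r0), so

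spurious difference = [p(IC) − p(ED)] × (r1 − r0).

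Only imbalance that survives weighting counts, and the sign may go either way. The documents give neither factor, so both are assumed: 10 to 50 points for the imbalance and 5 to 30 points for the risk difference. The benchmark is the plan's own (Section 7a): 50% − 27% = 23 points.

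- Lowest: 0.10 × 5 = 0.5 points; 0.5/23 = 2%.
- 0.20 × 10 = 2.0 points; 2/23 = 9%.
- 0.30 × 20 = 6.0 points; 6/23 = 26%.
- Highest: 0.50 × 30 = 15.0 points; 15/23 = 65%.

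**Step 4. Ask what would remove the whole hypothesized effect.** The risk ratio is 0.27/0.50 = 0.54, with inverse 1.85. The E-value is 1.85 + √(1.85 × 0.85) = 1.85 + 1.25, or about 3.1. A hidden confounder would need risk ratios of about 3.1 with both setting and admission, beyond the measured covariates.

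**Step 5. Primary outcome.** Assume that status shifts time to first dose by 10 to 30 minutes, with the same imbalance range. The bias is 0.10 × 10 = 1 minute to 0.50 × 30 = 15 minutes. Section 3 gives historical Hopkins means of 190 minutes (ED) and 57.7 minutes (IC), a gap of 132.3 minutes; 1/132.3 = 0.8% and 15/132.3 = 11%. That gap is only a rough yardstick: the ED figure runs from triage and the IC figure from arrival, the calendar periods differ, and neither mean is adjusted.

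No sample-size figure enters this check.

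**The case against.** The strongest reply is that confounding has not been shown. Status would have to be related both to setting and to outcome, and no section says that IC access depends on being an established patient, that people eligible by address mainly use the ED, or that established patients fare differently. That stands. A reader might infer that the IC-ED contrast *is* confounded with being an established patient; the documents do not support that.

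A reader might also cite the Section 3 remark that care suffers "especially when managed by clinicians, as in the ED, who are unfamiliar with them". That sentence describes the clinicians in the ED. It does not say that patients followed by the center do better in either setting. Familiarity with the patient may also be part of what the IC delivers. Status at enrollment, however, precedes the visit, so adjusting for it does not adjust away what happens during the visit.

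Three further points have weight:

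- Section 4a's description of recruitment may leave few participants whom the center has never seen. But being seen there is not the same as receiving regular care, and Section 5's address route does not require either.
- Distance and prior-year use are in the model, and the sensitivity analysis is aimed at this kind of risk. The proxies are incomplete within 60 miles, and that analysis gauges a bias without removing it. It is best kept for variables that cannot be measured.
- Established patients could be sicker or heavier users of care, in which case any bias would run against the IC. This is why no direction is claimed.

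One could suppose that status must already be asked at screening. Because the routes are alternatives, it need be established only for people beyond 60 miles.

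**Conclusion.** The point holds as a gap in measurement and adjustment. Regular-care status defines one route into the cohort, is missing from both lists that feed the weighting, and is only partly represented by covariates that are there. Residual confounding by it therefore cannot be excluded, and this bears on the study's central claim.

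Its size and direction are unknown. The illustrative range of 0.5 to 15 admission points, and of 1 to 15 minutes for the primary outcome, rests wholly on assumed inputs and on imbalance that remains after weighting. The upper ends need both inputs to be extreme. With an E-value near 3.1 for the hypothesized admission effect, the likelier harm is to the size and credibility of the estimate than to its existence. The item is worth adding because it is cheap and is best captured at enrollment; the plan is not in error for lacking it.

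**What to change.** 1. Add to the baseline list in Section 4a: receives regular care at this center at enrollment (yes/no), with one written definition used at all four sites.
2. Add the item to the individual-level covariates of Eq 1 and to the overall and within-region balance checks.
3. Tabulate IC and ED use within each status group and inspect overlap before weighting.
4. Repeat the primary and admission analyses in regular-care participants only, as a sensitivity analysis.

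The cost is one extra baseline question, new but trivial for people living within 60 miles, plus one covariate and one further analysis. No stated sample-size figure changes. The statistical downside is that if one status group rarely uses one of the settings, adding the item may make the weights more variable or expose poor overlap, which would trouble a population average effect. In that case the regular-care-only analysis can show the comparison where overlap exists, and the report should say to whom it applies.
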